### **10.20. Assessment of Efficacy**

Assessment of efficacy will be done on an exploratory basis. Quality of life, mobility and echo measurements will be collected and assessed as discussed in Sections 6.1 Objectives and 14.1. Endpoint Definitions.

## 10.21. Recording Data

The study will collect data using Oracle Clinical, an electronic data management system for clinical studies. Sites will enter data onto eCRFs within an Oracle Clinical database.

Data reported on the eCRFs shall be derived from source documents, which may include worksheets, QOL questionnaires, patient medical records, echo data, blood lab data, programmer printouts and device interrogation/save-to-media files. These source documents must be created and maintained by the investigational site team. Further detail on data management is provided in Section 16.2. Data Management.

## 11.1. Potential Risks

Medtronic follows rigorous Quality Assurance and Control procedures throughout the life of the product, from the research and development phase through the study phase and market release.

There are risks associated with the elevated night pacing:

**Table 9: Risks Related to Elevated Pacing**

Risk	Potential Patient Harm	Mitigation
Pacing at a sustained elevated rate that causes symptoms during the day or night	Increased risk of Dizziness, palpitations, heart racing, shortness of breath, difficulty sleeping	
At the time of enrollment, subjects will be evaluated to whether they can tolerate a pacing rate of 100bpm
 
Subjects will be instructed to call study team if they are experiencing symptoms
 
Symptoms will be gathered from subjects using phone calls following enrollment, 4 week, and 8 week clinic visits
 
A programming checklist will be used at enrollment, 4 week, 8 week, and Exit visits to ensure appropriate programming of the Sleep Function parameters

Pacing at a sustained elevated rate may initiate or make heart failure or AF or ischemia worse	Increased risk of chest pain, atrial arrhythmia, or ischemia	We are monitoring troponin and NT-proBNP levels for worsening heart failure and troponin for ischemia. If levels worsen the subject will have their elevated pacing therapy programmed Off
Mode-switch during atrial arrhythmia results in a higher ventricular non-tracking pacing rate because the lower rate is programmed to 100bpm	Increased risk of Dizziness, palpitations, heart racing, shortness of breath	Symptoms will be gathered from subjects using phone calls following enrollment, 4 week, and 8 week clinic visits

Pacing at a sustained elevated rate that causes symptoms following unscheduled clinic visits. (Any minor telemetry activation, such as reprogramming, magnet application, or CareLink transmission will suspend the Sleep Function and the pacer will start pacing at the programmed Lower Rate.)
	
Increased risk of Dizziness, palpitations, heart racing, shortness of breath
	
Subjects will be instructed to call study team if they are experiencing symptoms
 
Subjects will also be asked their heart rate, which the subject can read using a finger pulse oximeter monitor that will be given to them at Baseline to use
 
Centers will be trained to instruct subjects to come to center for unscheduled visits


Misleading information that could reasonably lead to incorrect pacing therapy. (Rate histograms will show a higher percentage of pacing at 100bpm. Clinicians not aware of the subject's participation in the study may program the Lower Rate back to pre-study values.)
	
No risk to the patient. May result in loss of usable data for the study.
	
Subjects will be given a REVAMP study ID card

Negative impact to device longevity due to change in the pacing rate to 100 bpm
	
Failure to come in for exit visit for device reprogramming may negatively impact device longevity by 20% over remaining lifetime of device. Premature battery depletion which could lead to early Explant/ revision procedure related harm (Infection, Thrombus, Embolus, Hematoma, Stroke, Pneumothorax, Hemothorax, Nerve Damage)
	
The Patient informed Consent will include warnings about the impact to battery life of the device, if the patient does not adhere to the study protocol for the 12 week follow up and exit visit

Missing or Misleading information leading to adverse operation of the device when used in combination with other features or devices within its system
	
Risk of additional unnecessary elevated pacing rates.
	
The Clinical Investigation Protocol and training material will include details about the device interactions and programming recommendations for this study

Additional information can be found in the Foreseeable Adverse Event List (FAL) in **APPENDIX C**.

Subjects who are pregnant are excluded from study participation. If a subject becomes pregnant during the study, she must notify the physician immediately.

There may be other discomforts and risks related to elevated night pacing and this study that are not foreseen at this time. The adverse event collection requirements in this study will ensure that risks associated with the study are adequately monitored.

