### 10.11. Randomization (4 Week Follow-Up)

Subjects will be assigned to a group at random during the randomization visit. Randomization will occur at 4 weeks.

Subjects will be randomized in a 2:1 ratio to the Elevated Night Pacing ON or to the Elevated Night Pacing OFF group.

Sites will receive this randomization assignment from the randomization schedule, which is automatically populated on the eCRF.

Procedures to be performed and data to be collected at Randomization include:

- Physical Assessment (including weight, heart rate, symptoms, and blood pressure)
- Medications
- NYHA Class
- MN Living with Heart Failure Questionnaire
- 6 Minute Walk Test
- Echo\*
- Blood Draw\*\*
- Randomization assignment
- Device Interrogation/ (initial)
- Save-to-Media (initial)
- Device Programming, see Table 7: Programming Recommendations at 4 Week Follow-Up
- Device Interrogation (final) - this needs to be completed at the end of the visit after programming has been completed
- Save-to-Media (final)
- Adverse Events (report new/assess ongoing AEs), Study Deviations, System Modifications, Device Deficiencies, Crossovers (as they occur)

\*The echo must be sent to the Echo Core Laboratory for analysis, with a copy of the echo remaining at the site. Details of the Echo Core Laboratory, type of echo to be performed, and the review process will be provided in an Echocardiography Handbook (provided under separate cover).

\*\* The blood sample must be sent to the Blood Core Laboratory for analysis. Details of the blood core lab and the blood draw process will be provided under separate cover.

For any subject who has an abnormal NT-proBNP, troponin or LVEF measurement as defined in the Safety Assessment (Section 10.19. Assessment of Safety) and the investigator elects to discontinue elevated night pacing, a subsequent visit will be necessary for the elevated night pacing to be programmed OFF if the subject was randomized to the elevated pacing ON arm. The subject should continue to be followed through the 12 week visit.

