## **10.15. Study Exit**

Subjects will be exited from the study for any of the following situations:

- Study completed
- Subject death
- Subject lost to follow-up
- Subject chooses to exit (i.e. revokes informed consent)
- Investigator withdraws subject
- Subject has intolerable symptoms that cannot be alleviated by reprogramming

A Study Exit eCRF needs to be completed for all subjects with the date and reason for the exit. The following should also be collected if applicable:

- Scheduled/Unscheduled Follow Up eCRF, if applicable
- Adverse Events, Study Deviations, System Modifications, Device Deficiencies

The finger pulse oximeter should be returned to the site at the study exit visit. After all study tests and procedures have been completed and just prior to subject exit from the study, the subject may be informed (verbally or in written form) of the subject's randomization assignment.

Following exit, subjects will continue to receive standard medical care and should be managed and followed per physician discretion. There will be no further required study-related follow-up visits for these subjects.

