### **10.19. Assessment of Safety**

As a feasibility study, the primary objective is to assess the feasibility of using elevated night pacing as a therapy for heart failure with preserved ejection fraction. This includes assessing the safety and tolerability of elevated night pacing, as described in Section 5.1. Background. Subjects who experience intolerable symptoms from the elevated pacing therapy and whose symptoms cannot be reconciled by reprogramming may have the elevated night pacing programmed OFF. NT-proBNP, troponin, assessed from peripheral blood samples and LVEF, as assessed by the echo, will be collected at Baseline and at the 4 week visit. Subjects with increases in NT-proBNP and troponin from Baseline to the 4 week visit should be monitored by the investigator for accompanying symptoms, including worsening heart failure and cardiac ischemia. Symptoms should be reported as adverse events and subjects will be considered for withdrawal from the study, at the discretion of the investigator. Subjects with 4 week LVEF < 45% whose baseline LVEF was at least 55% may also be considered for withdrawal from the study at the discretion of the investigator. NT-proBNP, troponin and LVEF will be further assessed as discussed in Section 10.11. Randomization (4 Week Follow-Up) and Section 14.1.2. Ancillary Safety Endpoint – NT-proBNP, troponin, LVEF. Further information on the collection of Adverse Events is discussed in Section 12.5. Reporting of Adverse Events.

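### Table 9 promises a pacing stop that 10.11 and 10.19 leave to the investigator, and the tolerability proportions score a stop with continued follow-up as tolerated

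*Protocol*

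**What the plan says.** **Stopping for safety.** Table 9 of the protocol lists marker monitoring as the mitigation for worsening heart failure or ischemia and gives the consequence without qualification: "If levels worsen the subject will have their elevated pacing therapy programmed Off". Section 10.11 covers a subject with an "abnormal NT-proBNP, troponin or LVEF measurement as defined in the Safety Assessment", and makes the stop conditional: if "the investigator elects to discontinue elevated night pacing, a subsequent visit will be necessary". Section 10.19 asks the investigator to watch subjects whose NT-proBNP and troponin have increased for accompanying symptoms, and adds that "subjects will be considered for withdrawal from the study, at the discretion of the investigator". Its only numeric criterion concerns LVEF: "Subjects with 4 week LVEF < 45% whose baseline LVEF was at least 55" per cent may also be considered for withdrawal.

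**What happens to a stopped subject.** After a stop under 10.11, "The subject should continue to be followed through the 12 week visit". Section 10.15.4 also prefers that randomized subjects stay in. For intolerable symptoms there are two texts. In 10.19, subjects "whose symptoms cannot be reconciled by reprogramming may have the elevated night pacing programmed OFF"; in 10.15, the list of situations that lead to study exit includes "Subject has intolerable symptoms that cannot be alleviated by reprogramming".

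**How tolerability is scored.** Protocol 14.1.1 and SAP 7.9.1 take the proportion remaining in the study, with an exact one-sided 95% lower bound. The variables are active4wk and active8wk. Any study exit, and any death judged related or of unknown relation, counts against the proportion. Pacing status does not enter. The 8 week set excludes subjects who could not tolerate, or withdrew from, treatment in the first 4 weeks.

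**The concern.** There are two separate problems.

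First, the risk table describes a mandatory safeguard that the operative sections do not contain. A site facing a modest NT-proBNP rise cannot tell whether it must stop pacing, may stop it, or should only monitor. The cross-reference from 10.11 to 10.19 does not settle this for NT-proBNP or troponin.

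Second, a therapy can fail a subject without the subject leaving the study, and 10.11 directs exactly that path. On that path the tolerability variable reads success. The SAP says it wants a conservative estimate. Protocol section 14 reads the week 4 to 8 ON/OFF results as evidence on longer-term tolerability, for subjects whose first 4 weeks were safe and tolerable. At stake is whether the week 8 ON-arm figure tells the reader how many subjects could stay on elevated pacing, or only how many kept attending.

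**Working it through.** **Step 1. The stopping texts side by side.**

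| Place | Trigger for NT-proBNP or troponin | Consequence |
|---|---|---|
| Table 9 | levels worsen, not quantified | pacing off, stated as certain |
| 10.11 | abnormal, defined by reference to 10.19 | pacing off if the investigator chooses |
| 10.19 | increase from Baseline, not quantified | monitor; withdrawal considered at discretion |

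The marker thresholds in Background 5.1 come from cited literature; no section adopts them as stopping limits. The Table 9 wording therefore conflicts with the other two sections.

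**Step 2. How each path is scored under SAP 7.9.1.**

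| Path | active4wk | active8wk |
|---|---|---|
| ON subject stopped on the week 4 result, followed as in 10.11 | 1 | 1 |
| Same subject withdrawn from the study before week 8, as 10.19 permits | 1 | 0 |
| Intolerable symptoms before week 4, exits as in 10.15 | 0 | not in set |
| Intolerable symptoms before week 4, switched OFF as in 10.19 and retained | 1 | not in set |

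Rows 1 and 2 describe the same clinical event with opposite scores at week 8. In row 4 the stop lowers neither proportion, but that row arises only if 10.19 is used instead of 10.15.

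**Step 3. Timing.** After Baseline, the first scheduled blood draw and echo are at the week 4 visit itself (Table 4). A stop based on those results comes after active4wk is fixed, so it can affect only active8wk. A marker-driven stop before week 4 would need an optional unscheduled draw (10.13).

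**Step 4. Size, as an illustration.** The documents give no expected stop rate and no target proportion, so there is no figure of the plan's own to reproduce.

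Inputs:
- Up to 30 paced subjects (protocol 14, SAP 6).
- 2:1 allocation (protocol 7), so 30 × 2/3 = 20 ON if all 30 are randomized, which is an assumption.
- Exact binomial interval with ALPHA=0.1 (SAP 7.9.1). This leaves 0.1/2 = 0.05 in the lower tail and so matches the planned one-sided 95% bound.
- Number of stops k, assumed. Every stopped subject is retained and nobody exits.

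Formula: the lower bound is the 0.05 quantile of a Beta(x, n − x + 1) distribution. For x = n it reduces to 0.05^(1/n), giving 0.05^(1/20) = 0.861 and 0.05^(1/30) = 0.905.

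| k | Week 8 ON, as written | Week 8 ON, on therapy |
|---|---|---|
| 0 | 20/20 (0.861) | 20/20 (0.861) |
| 1 | 20/20 (0.861) | 19/20 (0.784) |
| 2 | 20/20 (0.861) | 18/20 (0.717) |
| 4 | 20/20 (0.861) | 16/20 (0.599) |

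With 18 ON subjects and k = 2, the comparison is 18/18 (0.847) against 16/18 (0.690).

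For week 4, the arithmetic with 30 subjects is 30/30 (0.905) as written against 29/30 (0.851) or 28/30 (0.805) on therapy for k = 1 or 2. By steps 2 and 3, this needs symptom stops handled as in row 4, or a stop after an unscheduled draw.

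**Step 5. Stops from the week 4 sample.** These reflect exposure in weeks 0 to 4, so they should be shown apart. With 2 such stops and 1 later symptom stop among 20, the on-therapy proportion is 17/20 (0.656) overall and 17/18 (0.762) with those 2 left out.

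**The case against.** A reader might infer that the proportions can register no safety-driven stop at all. The documents do not support that: a stop followed by study exit counts as a failure, and SAP 7.9.1 counts every exit before the visit against the therapy whatever its reason.

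A reader might also infer that the 4 week figure, the one that helps decide whether to proceed, is materially inflated. That is not supported either. Scheduled marker and echo results come too late to move active4wk, and 10.15 routes unresolved intolerable symptoms to exit. Section 10.19 need not contradict this, because Table 4 allows device programming at an early exit, so switching OFF and exiting can happen together. The week 4 gap stays open because 10.19 does not say so.

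Further points on the other side are fair. Following stopped subjects is sound practice in a randomized study. Crossovers are recorded, marker changes and adverse events have their own analyses, and ON-arm adverse event rates in SAP 7.9.3 already use only time on elevated pacing. The SAP also permits extra exploratory analyses. Section 14's statement on longer-term tolerability is limited to subjects whose first 4 weeks were safe and tolerable, which arguably leaves out someone stopped on a week 4 sample.

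These points narrow the concern without removing it. None of the planned outputs states how many ON subjects were still on elevated pacing at week 8, and the optional sensitivity analysis in 7.9.1 covers ambiguous exits only.

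**Conclusion.** Both parts hold, within limits. The wording conflict between Table 9 and 10.11/10.19 is plain from the text. So is the missing definition for NT-proBNP and troponin, though it does not follow that a numeric trigger is required: investigator judgement is a legitimate rule if Table 9 says so.

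The scoring gap concerns pacing stops with the subject retained. Its main effect is on the week 8 ON-arm proportion, where one or two retained stops among 20 leave the reported lower bound unchanged while the on-therapy bound falls by 0.077 (0.861 − 0.784) or 0.144 (0.861 − 0.717). Those figures rest on an assumed k, no exits, and all 30 subjects randomized; they size the scoring gap, not the Table 9 conflict.

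No net direction of bias can be claimed, because treating every exit as a failure pulls the other way, and the choice between exit and follow-up may partly track severity. The endpoints are ancillary and have no success threshold, so the consequence is a tolerability figure that can be misread, not a wrong formal decision.

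**What to change.** **SAP 7.9.1.** Keep active4wk and active8wk as retention measures, including the ON/OFF comparison. Add a descriptive proportion of subjects still in the study and still receiving elevated pacing, at week 8 (ON arm) and at week 4 (all paced subjects), with the same exact lower bound. Count pacing programmed OFF for a marker, LVEF or intolerable symptoms as a failure. List stops triggered by the week 4 sample separately.

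**Protocol, at the next amendment.** Make Table 9 agree with 10.11 and 10.19, for example by stating that stopping is at the investigator's judgement. State in 10.15 and 10.19 whether intolerable symptoms lead to pacing OFF with follow-up or to exit.

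**Cost.** The SAP change is two derived flags and no extra tests, since crossovers are collected and interrogations are requested at a crossover (10.16). The reason for each stop must be recorded; the eCRFs are under separate cover, so whether it already is cannot be seen. The amendment needs sponsor and IRB approval at each site and re-training as necessary (16.5). The tolerability figure may look less favourable, and the week 8 measure describes the ON arm only, because an OFF subject cannot fail it.

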### **11.2. Risk Minimization**

Medtronic has minimized the risks to the subject by the following:

- Performing required laboratory and pre-clinical testing prior to the REVAMP clinical study.
- Implementing quality control measures into development and production processes.
- Providing guidelines for subject selection and evaluation, and subject inclusion and exclusion criteria.
- Providing adequate instructions and training.
- Selecting investigators that have demonstrated previous experience with the programming, interrogation, and monitoring of pacemaker devices.
- After enrollment in the REVAMP clinical study, at each protocol required follow-up, the investigator must evaluate the subject's health, assess for any adverse events, and interrogate the study device to verify appropriate study device function.

### **11.3. Potential Benefits**

Elevated pacing rates may offer no benefit. The potential benefits of having the elevated pacing ON for this 12 week study include:

- Improvement in exercise capacity
- Improvement in symptoms

Additionally, information collected from this study may assist in the design of new product(s)/therapy(ies) and/or instructions for use.

### **11.4. Risk-Benefit Rationale**

The risk for harm is minimal with this study as the pacing rate is within the FDA-approved programmable parameters of the Lower Rate and the Sleep Function, and pacing rates of 100 bpm can occur with activities of daily living. There are potential benefits to the subject, as listed in Section 11.3. Potential Benefits. Therefore, the study risk-benefit is acceptable.

---

## **12. Adverse Event Assessments**

Timely, accurate, and complete reporting and analysis of safety information for clinical studies are crucial for the protection of subjects. Medtronic has established procedures to ensure appropriate reporting of safety information.

### **12.1. Adverse Events**

Adverse Event definitions are provided in Table 10. To ensure that all AEs that are potentially relevant are collected, the following will be collected throughout the study duration, starting at the time of signing the Informed Consent Form:

- All system related AEs
- All programming related AEs
- All cardiovascular related AEs
- All Serious Adverse Events (SAEs), regardless of relatedness

In order to fully understand intolerable symptoms and mitigate any safety concerns about elevated night pacing, for any subject that exits the study because of intolerable symptoms, the enrolling site should report any associated programming related AEs. Reporting of these events to Medtronic will occur on an Adverse Event (AE) eCRF. Documented pre-existing conditions are not considered AEs unless the nature or severity of the condition has worsened.

For AEs that require immediate reporting (see Table 12), initial reporting may be done by phone, fax, or on the eCRF completing as much information as possible. The original completed AE eCRF must be submitted to Medtronic as soon as possible.

Each adverse event must be reported separately. Any medication, whether cardiovascular or not, associated with the treatment of an adverse event must be reported.

Subject deaths are also required to be reported. Refer to Section 12.6. Subject Death for Subject Death collection and reporting requirements.

### **12.2. Device Deficiencies**

Device Deficiency is defined as an inadequacy of a medical device with respect to its identity, quality, durability, reliability, safety or performance. Device Deficiencies will need to be collected in the study. Device Deficiency information will be collected throughout the study and reported to Medtronic.

### **12.3. Processing Updates and Resolution**

For any changes in status of a previously reported adverse event (i.e. change in actions taken, change in outcome, change in relatedness), information needs to be updated on, or added to the original AE eCRF. All adverse events must be followed until the adverse event has been resolved, is unresolved with no further actions planned, the subject dies or exits the study, or until study closure, whichever occurs first.

At the time of study exit, all collected adverse events with an outcome of "Unresolved" must be reviewed and an update to the original AE eCRF must be reported. At a minimum, if there are no changes to the description, relatedness, test and procedures or actions taken, the outcome must be updated to reflect "Unresolved at time of study exit".

